#### 5.5 Adherence Assessment

Adherence to the study regimen for the active group requires completion of ≥20 of the 30 prescribed treatment sessions, as determined from review of each subject's Daily Log and the device's memory.

Further, subjects must complete the Pre-study, Baseline and Post-Study requirements to be considered compliant. If a subject does not adhere to the study requirements they will be asked to provide a reason, which will be documented in the Case Report Form (TR-1155-FORM-10). During data analysis, this information will be reviewed by the Data Safety and Monitoring Board to determine if/how the data should be adjudicated (see 10.5).

## 5.6 Concomitant Medications

Concomitant medications are defined as any prescription or over-the-counter medication (including hormonal contraception, vitamins, food supplements, and herbal preparations) taken seven days prior to initiation of pre-study activity through completion of post-study activity. Subjects will be instructed not to take any new concomitant medications unless medically necessary. If the use of a new concomitant medication becomes necessary, the treatment must be recorded in the Case Report Form (TR-1155-FORM-10), including the name of the medication, dosage, route of administration, date, and indication for use.

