#### 4.2 Exclusion Criteria.

Subjects will be excluded from enrollment if they meet any of the following criteria:

- Less than 1 incontinence accident (leak) per day\*
- Severe incontinence as determined by self-reported >5 accidents per day
- Currently pregnant, may be pregnant, attempting to become pregnant, or delivery within previous 6 weeks
- Vaginal or pelvic surgery within previous 6 months
- Severe Obesity as defined by BMI >= 35
- Change in incontinence medication type or dosing within the last 3 months.
- History or symptoms of urinary retention, extra-urethral incontinence, overflow incontinence
- Pelvic pain/painful bladder syndrome
- Active urinary tract infection (UTI) or history of recurrent UTIs (more than three in a year), or recurrent vaginitis (bacterial/fungal)
- Tissues protruding outside the vagina at rest
- Presence of incontinence-associated dermatitis or other perineal skin disorders or lesions,
- Complete denervation of the pelvic floor
- Conductive inter-uterine devise (IUD/Coil) or metal implants in the abdominal or pelvic area, including the hip and lumbar spine,
- Chronic coughing
- Previous use of Interstim device or Botox for UI
- Implanted cardiac device, untreated cardiac arrhythmia or suffer from other heart problems.
- Cancer, epilepsy or cognitive dysfunction
- Underlying neurologic/neuromuscular disorder
- Impaired decision making, suicidal thoughts, or drug/alcohol dependence
- Lacks capacity to consent for themselves.

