#### Recruitment

\* During the baseline week subjects will be excluded if they average less than 1 urge incontinence episode per day (with or without a leak).

- Ads placed in social media and other forums to attract candidates to a website that describes the study. These ads will be places in the US without regional geographic targeting and use key words including "incontinence" and "bladder leaks"
- Email to a list of women with urge incontinence who had previously expressed interest in participating in a clinical study.
- Alternately, healthcare providers who become familiar with the study can direct candidates
  to the study. These candidates will go through the same screening as all candidates and
  the referring healthcare provider would not be considered a study investigator. It is
  permissible for the referring healthcare provider to assist the candidates with completion
  of screening/consent information and to forward the information to Elidah.
- TR-1155-FORM-14 identifies the language that will be used in recruitment messaging.

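### Outside the 4.2 exclusions, the protocol text has no stability rule, no instruction against starting, and no structured record for conservative or device-based incontinence treatments, so one begun after baseline would count as device effect.

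*Combined protocol and SAP*

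**What the plan says.** **Co-treatment during the study.** Section 5.6 sets out which co-treatments it governs: "Concomitant medications are defined as any prescription or over-the-counter medication (including hormonal contraception, vitamins, food supplements, and herbal preparations". Women are told to avoid new ones unless medically needed. Any new one goes on the Case Report Form, "including the name of the medication, dosage, route of administration, date, and indication for use". These are drug fields.

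**Before entry.** The only stability rule in 4.2 is also a drug rule: "Change in incontinence medication type or dosing within the last 3 months". Section 4.2 does bar some non-drug treatments: "Previous use of Interstim device or Botox for UI", "Vaginal or pelvic surgery within previous 6 months", and "metal implants in the abdominal or pelvic area, including the hip and lumbar spine".

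**What is collected.** A pre-study questionnaire covers incontinence-related medical history and views on treatment, with possible use in post hoc subgroups (5.3). The Daily Log has free space for notes (5.3). Section 9.5 ties neither to a rule about co-treatment.

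**Endpoint and design.** The primary measure is each woman's percent reduction in all leaks, stress and urge together, from baseline to the sixth week, averaged by group. A responder rate at a reduction of at least 50% may be added (9.5). There is no control or sham group (6.6).

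**Other stimulators.** Section 3.1 describes pelvic-floor stimulation as effective for urge incontinence and names cleared vaginal devices. The marketed ELITONE is sold over the counter (6.1), and its output has a 50 Hz and a 10 Hz part, which 6.5 links to stress and urge incontinence respectively.

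**The concern.** The plan asks a woman not to begin a new vitamin and records it if she does. It has no matching provision for a second pelvic-floor stimulator or a course of pelvic-floor training, which by the protocol's own background could act on the endpoint.

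In a controlled trial such co-treatment would tend to occur in both arms. Here each woman is her own comparison, so whatever lowers her leaks between baseline and week 6 is read as ELITONE-UUI effect. Because the endpoint is total leaks, relief of stress leakage by another treatment counts as well. The data are meant to support FDA clearance (6.7, 9.6), and 9.1 names a 50% mean reduction and/or a 50% responder rate as the level the sponsor expects to suffice. Without dates of starting and stopping, an affected result would be hard to examine afterwards.

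**Working it through.** No figure in the plan is in dispute. The check is a reading of the text, followed by an illustration of size.

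**1. Which treatments are covered**

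| Treatment | Entry rule (4.2) | 'Do not start' (5.6) | Structured record (5.6) |
|---|---|---|---|
| Incontinence drugs | unchanged for 3 months | yes | yes |
| Other drugs, vitamins, supplements | none | yes | yes |
| Interstim, Botox | any previous use excluded | – | – |
| Vaginal or pelvic surgery | excluded within 6 months | – | – |
| Pelvic-floor or bladder training, physiotherapy | none | none | none |
| Vaginal or surface stimulators, marketed ELITONE | none | none | none |

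The gap is the last two rows.

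**2. Direction of bias.** Percent reduction = (B − F)/B × 100, where B is the baseline and F the final-week average.
- *Unchanged co-treatment.* If it multiplies leaks by the same factor c in both periods, (cB − cF)/(cB) = (B − F)/B. It cancels exactly under this assumption, and largely otherwise.
- *Started or intensified after baseline.* Only F falls, so the reduction is inflated.
- *Stopped shortly before baseline, with residual effect.* B is too low. Assume true values of 2.0 and 1.2 per day: (2.0 − 1.2)/2.0 = 40%. With B 20% too low, at 1.6: (1.6 − 1.2)/1.6 = 25%. The reduction is understated.

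**3. Size on the responder rate.** Inputs: 20 women per group and the 50% level (9.1), hence at least 10 of 20. One woman is 1/20 = 5 points. Assumed: a true device responder rate p, and one woman who starts a co-treatment.
- No co-treatment: P(X ≥ 10), X ~ Bin(20, p).
- One certain responder: the other 19 must supply 9, so P(X ≥ 9), X ~ Bin(19, p).
- She responds with probability 0.75 (assumed): 0.75 × P(X ≥ 9) + 0.25 × P(X ≥ 10), X ~ Bin(19, p).

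| p | None | One, certain | One, probability 75% |
|---|---|---|---|
| 40% | 24.5% | 33% | 29.6% |
| 45% | 40.9% | 50.6% | 46.2% |
| 60% | 87% | 91% | 89% |
| 75% (prior series, 9.1) | 99.6% | 99.8% | 99.6% |

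For p = 45% the last column is 0.75 × 0.506 + 0.25 × 0.329 = 0.462.

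**4. Size on the primary measure.** If one of 20 women moves from an assumed 40% to 75% reduction, the group mean moves by (75 − 40)/20 = 1.75 points.

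**The case against.** Four stronger readings are tempting, and the documents do not support them.

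- *No non-drug treatment is excluded.* Section 4.2 excludes Interstim, recent pelvic surgery and regional metal implants. The gap is confined to conservative and other device-based treatments.
- *Any co-treatment inflates efficacy.* Unchanged use largely cancels, and carry-over from a stimulator stopped before baseline works against the device. Only starting or intensifying after baseline inflates the result.
- *Such use is likely in this population.* Recruitment includes "Email to a list of women with urge incontinence who had previously expressed interest in participating in a clinical study" and advertisements keyed to incontinence, but neither shows concurrent use of another treatment. Section 3.1 says two thirds of affected women go untreated, and the discounted deposit in 4.4 appeals mainly to women who do not own the device. No rate can be inferred.
- *Nothing is recorded, so nothing can be examined.* The screening questions, questionnaires, Daily Log, user manual and subject instructions are separate documents and were not available. They may ask about or restrict such treatments. The statement holds for the protocol text only.

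It is also fair to say that the illustration is most sensitive close to 50%, that the responder rate is an additional rather than the primary summary, and that at least 10 of 20 is not a formal test in a study described as not hypothesis driven. All of this stands and limits the size. It does not close the gap: the one upward mechanism is credited to the device, and the protocol provides neither a control group nor a structured record with which to separate it.

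**Conclusion.** The concern holds in this limited form. For conservative and device-based treatments outside the 4.2 exclusions, the protocol text sets no stability requirement, does not ask women to refrain from starting, and requires no structured record. A treatment begun or intensified after baseline is counted as device effect.

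The size is unknown because the documents give no rate of use. For one such woman in a group of 20 it is up to 5 points of responder rate. It matters if the true rate lies just under 50% (41% to between 46% and 51% at an assumed 45%) and is negligible if the rate is near the prior series' 75%. The effect on the group mean is about 1.75 points under the stated assumption. These figures rest on assumed true rates, an assumed single co-treated woman and an assumed probability that she responds. The change is worth making because it is cheap and the information is hard to recover afterwards.

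**What to change.** - **5.6:** widen the section from medications to all incontinence treatments. Ask women not to start or change a non-drug incontinence treatment (pelvic-floor or bladder training, physiotherapy, another stimulator, the marketed ELITONE) between baseline and study end. Record current use at entry, and any start, stop or change with dates, on the Case Report Form. If the separate forms already do this, refer to them here.
- **9.5:** add a prespecified sensitivity line for both summaries. Count women who started or intensified such a treatment as non-responders in the responder rate, and leave them out of the mean percent reduction. Report how many there were in each group.
- **4.2:** whether to add an entry exclusion or a stability window for these treatments is for the sponsor to decide. The recording and the sensitivity line are useful either way.

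The cost is a little extra data collection and one more analysis line, which may show a less favourable figure.

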# Screening

- Interested candidates complete an online survey comprising Screening Questions (TR-1155-FORM-13)
- Responses are maintained electronically in a Screening Log (TR-1155-FORM-11) which includes candidate contact information, date of survey completion, and survey responses.
- Survey responses will be reviewed to confirm that (based on IP addresses and/or provided contact info) candidates did not complete the survey multiple times with different responses, potentially in an attempt to qualify for enrollment.
- Hardcopy or verbal responses are acceptable and will be manually entered into the Screening Log.

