## 5.3 Description of Evaluations

This research utilizes validated methods for evaluating the clinical impact of the device/treatment, including several identified in the FDA guidance document regarding clinical studies that investigate urinary incontinence. Urinary incontinence episodes per day data, obtained from the subject's Daily Log, serves as the primary efficacy outcome measure (see 2.2). Analysis of adverse events serves as the primary safety outcome measure (see 2.2). Evaluations utilized throughout the study are described below. See 9.5 for detail regarding strategies for analyzing the data obtained in these evaluations.

- I-QoL Questionnaire (Pre- and Post-study) the Incontinence Quality of Life (I-QoL) questionnaire is validated tool for assessing changes in the degree to which urinary incontinence affects a woman's quality of life (TR-1155-FORM-2). It comprises 22 questions, to which the subject provides a numeric response on a 1-5 scale. The score is the sum of the numeric responses, which can range from 22 to 110. A change of 2.5 points is considered clinically significant. The I-QoL questionnaire is provided to the subjects as part of pre- and post-study materials. Completed questionnaires are returned to Elidah via mail or electronically (see 10.4).
- Pre-Study Incontinence History and Usability Questionnaire (Pre-study) Included in
  the pre-study activity is a questionnaire that investigates each subject's medical history as
  it pertains to incontinence as well as their perceptions and preferences regarding
  incontinence treatments (TR-1155-FORM-1). Some of this information may be utilized in
  post hoc subgroup analysis (see 9.5). It may also be useful in informing strategies for
  Elidah to effectively reach potential patients.
- Daily Log (Baseline week and treatment weeks) Subjects are required to maintain a

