# 9.5 Data Analyses

This is not a hypothesis driven study. Descriptive statistics will be the primary means of data analysis. Comparison between the treatment groups may be made to, in part, support Elidah's selection of a preferred configuration for eventual product commercialization. However, this case series study is not designed to allow rigorous statistical analysis between the groups.

Electrical stimulation is known to have a positive effect on both UUI, and some women have difficulty distinguishing between UUI and SUI episodes. Accordingly, in an effort accurately capture the totality any therapeutic improvement, the study's **primary outcome measure** of efficacy is a change in total urinary incontinence (UI) leaks, both SUI and UUI. Each adherent subject's Daily Log will be used to determine the average number of urinary incontinence episodes per day for the baseline and 6th week (see 5.5 regarding subject adherence). To accommodate the likelihood that some subjects will omit log data, the "weeks" referred to in the baseline and 6th week assessments refer to the first and last 5 entries in the Daily Log. The percent reduction in UI episodes is then calculated for each patient by subtracting the final week average from the baseline average, dividing the difference by the baseline average, and multiplying by 100. The percent reductions for each patient are then used to define an average (and standard deviation) reduction for each treatment group.

UI episodes per day data may additionally be reported as a responder rate. FDA guidance suggests that subjects with a percent reduction of  $\geq$ 50% be considered responders. Accordingly, the responder rate for each treatment group will be calculated by dividing the number of subjects with a reduction of  $\geq$ 50% by the total number of subjects.

**Secondary outcome measures** will similarly use descriptive statistics (e.g. mean, standard deviation) to characterize changes from baseline. Additionally, where applicable, FDA suggested response rate thresholds will be referenced. Notes on specific secondary outcome measures include:

- Change in urgency episodes with a leak UUI leak data will be analyzed in the same manner as the primary outcome measure data.

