- Change in urgency episodes without a leak Differences in mobility, activity, etc. may impact whether a subject can get to a toilet before an urgency leak occurs. Analysis of episodes without leaks will occur in the same manner as the "with leak" data.
- Change in pad use Reduction in pad usage will be assessed as a percent change relative to the baseline, and as a response rate, wherein a 50% reduction is considered clinically significant. Subjects who do not use a pad during the baseline week will be excluded from the analysis.
- Change in daily bathroom visits / Change in nighttime bathroom visits Descriptive statistics as defined above.
- I-QoL Incontinence Quality of Life scores will be analyzed with respect to a change from baseline. Responders will be those with an I-QoL score increase of 2.5 points, which is defined in the FDA guidance as clinically significant.

Usability surveys will solicit subject feedback pertaining to their experience with the product. Appropriate statistical methods will be used in reporting these subjective measures.

In addition to characterizing outcome measures as a change in value/score (i.e. percent reduction) or a clinically meaningful response (e.g. ≥50% change), post hoc analyses may investigate outcome measures using analysis of covariance (ANCOVA), wherein baseline values are modeled as covariates, which has the advantage of accounting for variation in the magnitude

of the baseline. Additional post hoc ANCOVA may be performed with covariates including age, type of incontinence, BMI or other potentially relevant variables.

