## 10.6 Quality Assurance

Training –The Clinical Director is responsible for ensuring that the study staff can perform
the responsibilities they have been assigned. All study staff will be required to complete
the NIH Protection of Human Subjects Training before performing any function of the
study.

- Quality Control Committee Given to the small scope of the study, a Quality Control
  Committee will not be utilized. The Clinical Director has responsibility pertaining to
  maintenance of study quality, and the Data Safety and Monitoring Board exists to ensure
  appropriate human protection regulations are met and adverse events are appropriately
  handled.
- Metrics Section 9.5 defines that data analysis and statistical approach used to determine study success. Upon completion of the analysis one or more persons not involved with the original data analysis will audit the data entry, mathematical calculations and statistically driven conclusions.
- **Protocol Deviations** Protocol deviations will be documented using Protocol Deviation Log (TR-1155-FORM-8) and retained within the Study Binders. The Clinical Director and/or Data Safety and Monitoring Board will make the determination of whether the impact of the deviation should be considered in subsequent analysis.

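### Section 5.6 restricts and records only new drugs, so a dose change or stop of an existing incontinence drug during the study may go unrecorded

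*Combined protocol and SAP*

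**What the plan says.** The exclusion criteria (4.2) rule out a woman with a "Change in incontinence medication type or dosing within the last 3 months". Dosing is named alongside type. A woman whose drug and dose have been steady for longer than that is not excluded on this ground.

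Section 5.6 defines concomitant medication broadly. It covers prescription and over-the-counter products from seven days before pre-study activity until post-study activity ends, so an existing incontinence drug falls within the definition. The two rules that follow are narrower. Women are told to avoid *new* medications unless medically necessary. If a new "concomitant medication becomes necessary, the treatment must be recorded in the Case Report Form (TR-1155-FORM-10), including the name of the medication, dosage" and further details follow.

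The primary measure (9.5) is each woman's percent reduction in leaks per day from baseline to the sixth week, averaged within each group. Section 9.5 adds that "UI episodes per day data may additionally be reported as a responder rate". Section 6.6 states that there is no control or sham group.

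**The concern.** At entry, the plan treats a recent dose change as reason enough to exclude a woman. Once she is in, the same change meets no rule. Raising, lowering or stopping a drug that she already takes is not taking a new one, so 5.6, followed to the letter, neither discourages it nor asks for a record.

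This matters because efficacy rests on an uncontrolled before-and-after comparison. A drug change between the baseline log and the final log entries acts on the same leak counts as the device, and no control group shares that influence. An increase in dose would usually flatter the device, and a cut or stop would usually count against it. If the change was not recorded, nobody can later see which women were affected.

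**Working it through.** **1. The rules side by side**

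| Event | At entry (4.2) | During the study (5.6) |
|---|---|---|
| New incontinence drug, or switch to a different one | Excludes if within 3 months | Discouraged unless medically necessary; recorded |
| Dose of an existing drug raised or lowered | Excludes if within 3 months | Not mentioned |
| Existing drug stopped | Plausibly a change in type or dosing, so excludes | Not mentioned |

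**2. Could another section close the gap?**

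- 5.5: for a woman who does not adhere to study requirements, a reason is documented and "this information will be reviewed by the Data Safety and Monitoring Board to determine if/how the data should be adjudicated". No requirement concerns dose stability, so a dose change need not reach this step.
- 10.6: for protocol deviations, the Clinical Director and/or the board "will make the determination of whether the impact of the deviation should be considered in subsequent analysis". A dose change departs from nothing that the protocol states.
- 8: the listed reasons for discontinuing a woman do not include a medication change.
- 9.5: "Additional post hoc ANCOVA may be performed with covariates including age, type of incontinence, BMI or other potentially relevant variables". This is optional, and it cannot use a change that nobody recorded.
- 4.3 and 5.3: at screening, "Interested candidates complete an online survey comprising Screening Questions (TR-1155-FORM-13"), and included in "the pre-study activity is a questionnaire that investigates each subject's medical history as" it relates to incontinence. Both come before treatment, so neither can capture a later change. They may well record drugs in use at baseline. The forms are not shown, and nothing here concerns baseline capture.
- 5.3: the Daily Log has free space for notes. Medication changes are not among the items named, but that list is not complete.
- 7.3 and 7.4: adverse events include a baseline symptom that worsens, are recorded whatever their cause, and are also looked for in routine contact and log review. A dose raised because leakage worsened, or a drug stopped for a side effect, would often come with a recordable event. The drug change itself is not a required item.

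The last two routes are partial and incidental. None of these sections requires the record.

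**3. Scale**

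Inputs: 20 women per group, 40 in total (5.2); pooling is possible (9.6).

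- Responder rate, one woman's status changed: 1/20 = 5 points; pooled, 1/40 = 2.5 points.
- Mean percent reduction, one woman's value shifted by x points: x/20. For assumed x = 20, 40, 60 this gives 1, 2, 3 points; pooled, x/40 gives 0.5, 1, 1.5 points.

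The values of x and the count of one woman are illustrations. The documents give neither the number of drug users nor a rate of change.

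**4. What a summary without one affected woman would do**

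Take the level of the prior 20-subject series in 9.1: mean reduction 72%, responders 75% (15/20).

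- Omit a woman with a 100% reduction: (20 × 72 − 100)/19 = 1340/19 = 70.5%; responders 14/19 = 73.7%.
- Omit a woman with no reduction: (20 × 72 − 0)/19 = 1440/19 = 75.8%; responders 15/19 = 78.9%.

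The figure can move either way. This is the leverage of any one woman among 20 and is not specific to medication.

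**The case against.** The strongest reply is that this is a small wording gap with no demonstrated effect. Changes should be rare: entry requires 3 months of stability, the course lasts 6 weeks, and 3.1 remarks that women often do not want these drugs. The study is declared descriptive (2.3, 9.5), so no test is affected. Adverse-event reporting would often surface the changes most likely to alter leakage. The Daily Log, post-study questionnaire, Case Report Form and subject instructions are not shown, and any of them might hold a medication item or a stable-dose instruction. All of this stands, and it limits the weight of the point. It does not remove the gap, because the protocol text still does not require the record.

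Three stronger readings are tempting, and the documents do not support them.

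- A reader might infer that new drugs are dealt with at analysis while changes to existing ones are not. In fact 5.6 permits a medically necessary new drug, so its use breaks no requirement and need not trigger 5.5 or 10.6 either. The difference that 5.6 makes is the instruction and the Case Report Form entry.
- A reader might infer that the gap favours the device. The direction depends on whether doses rise or fall, and nothing in the documents says which is likelier.
- A reader might infer that one unrecorded change could turn success into failure at 50%. That needs a group sitting at 50%, which nothing predicts. Section 9.1 states only what the sponsor anticipates will be adequate for clearance, not a pass/fail rule.

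**Conclusion.** The point holds as a gap in a stated rule. Section 4.2 treats a dose change as disqualifying, and 5.6 then covers only new drugs. A dose change or stop during the study may therefore go unrecorded, and without a sham group its effect is counted in the before-and-after result as device effect, in either direction.

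The size is modest: 5 points on a group's responder rate per woman whose status changes, or 2.5 points if 40 are pooled. The frequency is unknown and probably low. The conclusion rests on the protocol text alone; an item on one of the forms not shown could narrow or close the gap in practice. No test or decision rule changes. This is a cheap improvement to consider, not a flaw that undermines the study.

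**What to change.** In 5.6, instruct women to keep incontinence drugs at a stable dose unless a change is medically necessary. Require any start, stop or dose change, with its date, to be recorded on the Case Report Form through post-study, using one item on an existing form such as the Daily Log or post-study questionnaire.

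In 9.5, leave the primary analysis unchanged and list the affected women with their results by group. Any summary that omits them should be labelled supportive only. A woman may raise her dose because the device did not help, or stop because it did, so leaving her out selects on something that may follow from treatment response.

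The cost is about two sentences in 5.6, one or two in 9.5, one added form item and a short listing. No visit is added.
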